6.2. Disposition

The study populations summary will use the All Subjects Enrolled (ASE) population and show the number of subjects overall who were enrolled, the number of screen failures and the number with each reason for screen failure. It will also show the number of subjects who were randomised and who were in the mITT, Safety and PK populations.

For the mITT population, two tables will be produced showing reasons for withdrawal from study and reasons for withdrawal from treatment. These summaries will show the number and percentage of subjects who completed the treatment/study, who withdrew prematurely and who reported each primary and sub-reason for withdrawal.

6.3. Medical Conditions

The number and percentage of subjects reporting each current medical condition will be presented. This table will include a subheading of 'Cardiovascular Risk Factors,' which will summarise the information taken from the cardiac disorders page in the eCRF. All medical conditions must be summarised on this table regardless of frequency. This will be repeated for past medical conditions.

6.4. Concomitant Medications

Non-Asthma medications will be summarised by Anatomical-Therapeutic-Chemical (ATC) level 1 and ingredient. Asthma medications will be summarised by the latest version of the Respiratory Medication Class (RMC), and will be derived for each asthma concomitant medication. Multi-ingredient medications will be presented according to their combination ATC classification rather than the classifications of the ingredients.

Asthma and non-asthma medications will be listed together. A listing of the relationship between ATC Level 1, ingredient and verbatim text will be produced for non-asthma medications only.

7. EFFICACY ANALYSES

Due to low subject numbers no statistical analysis will be performed.

7.1. Primary Efficacy Analyses

7.1.1. Endpoints and Summary Measures

Primary Endpoints	Summary Measure
Change from baseline (Week 0) in blood eosinophils over time	Summary statistics (raw and change from baseline)
Change from baseline (Week 0) in fractional exhaled nitric oxide over time	Summary statistics (raw and change from baseline)

Primary efficacy summaries will be based on the mITT population and no intercurrent events will be considered.

7.2. Secondary Efficacy Analyses

7.2.1. Endpoint and Summary Measure

Secondary Endpoints	Summary Measure

 Change from baseline (Week 0) in spirometry parameters over time including but not limited to pre-bronchodilator Forced expiratory volume in 1 second. Change from baseline (Week 0) in Asthma Control Questionnaire -5 absolute score at Weeks 2, 4, 8 and 12 Change from baseline (Week 0) in Asthma Quality of Life Questionnaire total and domain scores at Weeks 2, 4, 8 and 12 	Summary statistics (raw and change from baseline)

 Proportion of responders to ACQ-5. A responder to ACQ-5 will be defined as a subject who has a decrease from baseline in ACQ-5 score of 0.5 or more at Weeks 2, 4, 8 and 12. Proportion of responders to AQLQ. A responder to AQLQ will be defined as a subject who has an increase from baseline in AQLQ score of 0.5 or more at Weeks 2, 4, 8 and 12. 	Number and percentage of responders

Secondary efficacy summaries will be based on the mITT population and no intercurrent events will be considered.

8. SAFETY ANALYSES

The safety analyses will be based on the Safety population, unless otherwise specified. The details of the planned displays are provided in [Appendix 10: List of Data Displays](#).

8.1. Adverse Events Analyses

Adverse events analyses including the analysis of adverse events (AEs) and Serious (SAEs) will be based on GSK Core Data Standards.

8.2. Vital Signs, Electrocardiogram (ECG) and Holter

Summary statistics for vital signs at baseline, Weeks 0, 4, 8, 12, and 24 will be produced along with change from baseline summaries for each post baseline timepoint. In addition, the change between post-dose and pre-dose vital signs measurements will be summarised at weeks 0, 4 and 8.

A summary of ECG findings along with a table that shows the maximum increase in QTcF values post-baseline relative to baseline category will be produced.

In addition a summary of Holter interpretations will be produced for participants with at least 16 hours of data, however all data will be listed.

8.3. Clinical Chemistry, Haematology and Cardiac Markers

A summary of worst case clinical chemistry results relative to the normal range post-baseline, will be produced. Similar tables will be created for haematology and cardiac markers.

8.4. Antibodies

Summaries of the incidence of and titres of anti- GSK3772847 antibodies at weeks 0*, 2, 4*, 8*, 12 and 24.

* = Pre-dose only

8.5. Clinical Laboratory Analyses

Laboratory evaluations including the analyses of liver function tests will be based on GSK Core Data Standards.

9. PHARMACOKINETIC ANALYSES

Due to low subject numbers no statistical analysis will be performed.

9.1. Secondary Pharmacokinetic Analyses

Serum concentrations of GSK3772847 will be summarised by nominal time.

Pharmacokinetic summaries will be based on the Pharmacokinetic population, and no intercurrent events will be considered.

10. PHARMACODYNAMIC AND BIOMARKER ANALYSES

10.1. Secondary Pharmacodynamic Analyses

Summary statistics of raw and percentage change from baseline in free and total soluble ST2 levels (serum) will be produced.

Pharmacodynamics summaries will be based on the mITT population, and no intercurrent events will be considered.

12. APPENDICES

12.1. Appendix 1: Protocol Deviation Management and Definitions for Per Protocol Population

The full list of protocol deviations collected on the eCRF is in the Protocol Deviation Management Plan (PDMP). Please refer to this document for current guidance.

There is no per protocol population in this study.

12.2. Appendix 2: Schedule of Activities

12.2.1. Protocol Defined Schedule of Events

Procedure	Screening (±5days)	Run-in (±5days)	Treatment Period (Visit window ±3days)				End of Treatment / EW (±3days)	FU (±3days)	Notes
			V3	V4	V5	V6			
Visit	V1	V2	V3	V4	V5	V6	V7	V8	
Week	-4	-2	0	2	4	8	12	24	
Day	-28	-14	1	15	29	57	85	169	
Informed consent	X								May be obtained prior to Screening.
Inclusion and exclusion criteria	X	X	X						Recheck clinical status before 1 st dose of study medication.
Demography	X								
Full physical examination	X								To include height and weight
Medical/medication/ drug/alcohol/smoking history	X								Including smoking history, substance abuse, medical conditions and family history of premature cardiovascular disease; asthma disease duration and exacerbation history
Human immunodeficiency virus (HIV), Hepatitis B and C screening	X								If test otherwise performed within 3 months prior to first dose of study treatment, testing at screening is not required
Genetics									
Informed consent for Pharmacogenetic blood sample		X							

Procedure	Screening (±5days)	Run-in (±5days)	Treatment Period (Visit window ±3days)				End of Treatment / EW (±3days)	FU (±3days)	Notes
			V3	V4	V5	V6			
Visit	V1	V2	V3	V4	V5	V6	V7	V8	
Week	-4	-2	0	2	4	8	12	24	
Pharmacogenetic (PGx) blood sample			X						PGx sample may be drawn any time from Visit 3 onwards, pre-dose. Informed consent must be obtained before collecting a sample.
Study Treatment and Questionnaires									
Randomisation			X						
Study treatment			X		X	X			
Dispense diary card		X							To be completed daily.
Diary card review			X	X	X	X	X		
Collect diary card							X		
Rescue medication dispensing		X	X ¹	X ¹	X ¹	X ¹			1. As needed
ACQ-5	X		X	X	X	X	X		Test to be performed before all other assessments
AQLQ			X	X	X	X	X		Test to be performed immediately after ACQ-5
Efficacy									
Haematology (including eosinophil count)	X		X ¹	X	X	X	X		1. Pre-dose
FeNO	X		X	X	X	X	X		Test to be performed pre-dose
Spirometry	X		X	X	X	X	X		Test to be performed pre-dose

Procedure	Screening (±5days)	Run-in (±5days)	Treatment Period (Visit window ±3days)				End of Treatment / EW (±3days)	FU (±3days)	Notes
			V3	V4	V5	V6			
Visit	V1	V2	V3	V4	V5	V6	V7	V8	
Week	-4	-2	0	2	4	8	12	24	
Free and total sST2 (serum)			X ¹	X	X ²	X ¹	X ³	X ³	1. Pre and Post Dose 2. Pre Dose 3. Anytime (± 5 days) Pre-dose samples: within 2 hours from the planned dosing time Post-dose samples as soon as possible after end of infusion but must be taken within 4 hours.
Total & fungal specific IgE	X ¹		X ²	X	X	X	X		1. Fungal specific IgE only if no historical documented results available 2. Pre-dose

Procedure	Screening (±5days)	Run-in (±5days)	Treatment Period (Visit window ±3days)				End of Treatment / EW (±3days)	FU (±3days)	Notes
			V3	V4	V5	V6			
Visit	V1	V2	V3	V4	V5	V6	V7	V8	
Week	-4	-2	0	2	4	8	12	24	
Induced sputum sample for biomarkers		X	X ¹²				X ³		
 1. If no viable sample is produced at V2, induction should be repeated pre dose at V3 2. If a participant does not produce a viable baseline sputum sample at visit 2 or at visit 3, the participant will not need to undergo a sputum induction at the end of the treatment period. 3. If no viable sample is produced, induction should be repeated after a minimum of 72 hrs but no later than 7 days after scheduled visit.

Procedure	Screening (±5days)	Run-in (±5days)	Treatment Period (Visit window ±3days)				End of Treatment / EW (±3days)	FU (±3days)	Notes
			V3	V4	V5	V6			
Visit	V1	V2	V3	V4	V5	V6	V7	V8	
Week	-4	-2	0	2	4	8	12	24	
Pharmacokinetics									
Serum blood sample for PK			X ¹	X	X ²	X ³	X ⁴	X ⁴	1. Post Dose 2. Pre Dose 3. Pre and Post Dose 4. Anytime (± 5 days) Pre-dose samples: within 2 hours from the planned dosing time Post-dose samples as soon as possible after end of infusion but must be taken within 4 hours.
Safety									
Laboratory assessments	X ^{1,2}		X ^{1,3}	X ¹	X ^{1,3}	X ¹	X ^{1,3}	X ¹	1. Clinical chemistry (includes liver chemistry) 2. Routine urinalysis at screening (Visit 1) 3. Cardiac markers Note: haematology assessments in efficacy section
Serum blood sample for immunogenicity			X ¹	X	X ¹	X ¹	X	X	1. Pre Dose

Procedure	Screening (±5days)		Treatment Period (Visit window ±3days)				End of Treatment / EW (±3days)	FU (±3days)	Notes
	V1	Run-in (±5days)	V3	V4	V5	V6	V7	V8	
Week	-4	-2	0	2	4	8	12	24	
Urine or serum pregnancy test (WOCBP only)	X ¹		X		X	X	X	X	To be performed pre-dose during the treatment period 1. Serum pregnancy test required
12-lead ECG	X		X ¹		X ¹	X ¹	X		1. Test to be performed pre-dose and post-dose within 30 mins after end of infusion.
24 hour Holter		X	X ¹						Holter monitor needs to be returned to the clinic at end of 24 hour recording (i.e. the next day). ¹ Place the Holter 30-60mins prior to dosing
Vital signs	X	X	X ¹		X ¹	X ¹	X	X	1. Test to be performed prior to the 12-lead ECG (pre-dose and post dose)
AE review			←=====→						
SAE review	X	X	←=====→						At V1 and V2 collect only SAEs considered as related to study participation.
Concomitant medication review	X	X	←=====→						

EW: Early Withdrawal. The list of assessments listed in this column should be completed for an early withdrawal visit.

12.3. Appendix 3: Assessment Windows

12.3.1. Definitions of Assessment Windows for Analyses

Nominal visits will be used and no windowing will be applied for analysis.

12.4. Appendix 4: Study Phases and Treatment Emergent Adverse Events

12.4.1. Study Phases

Assessments and events will be classified according to the time of occurrence relative to study treatment start date.

Study Phase	Definition
Pre-Treatment	Date ≤ Study Treatment Start Date
On-Treatment	Study Treatment Start Date < Date ≤ Study Treatment Stop Date + 28 days
Post-Treatment	Date > Study Treatment Stop Date + 28 days

Completion of study epochs will be defined as the following:

Study Phase	Definition of Completion
Run-in	Randomised into study and received first dose of study treatment
Treatment	Completed Week 12 visit
Follow up	Completed 12 week follow-up period

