To evaluate the safety and tolerability of GSK3772847 compared with placebo in moderate to severe asthma participants with AFAD	
Safety and tolerability parameters include:
 
 • Treatment emergent adverse events (AE) • Clinical Laboratory safety data • Vital signs (blood pressure, heart rate) • 12-Lead Electrocardiogram (ECG) monitoring • 24-hour Holter monitoring
Exploratory Objectives	Exploratory Endpoints
To evaluate changes in exploratory biomarkers in the blood of moderate to severe asthma participants with AFAD who have been treated with GSK3772847 compared with placebo	
 • Change over time in levels of serum total Immunoglobulin E (IgE), fungal-specific IgE
To evaluate changes in IL-33 related and disease biology biomarkers in the sputum of moderate to severe asthma participants with AFAD who have been treated with GSK3772847 compared with placebo	
 • Difference from placebo in levels of sputum biomarkers including but not limited to interleukin (IL)-33, IL-13, IL-4, IL-5 and TNF- α • Difference from placebo including but not limited to levels of sputum eosinophils

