12.4.3. Treatment Emergent Flag for Adverse Events

Flag	Definition
Treatment Emergent	
If AE onset date is on or after treatment start date & on or before treatment stop date + 28 days.
 
Study Treatment Start Date ≤ AE Start Date ≤ Study Treatment Stop Date + 28 days

NOTES:

- If the study treatment stop date is missing then the AE will be considered to be On-Treatment.

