12.7.2.1. Handling of Missing and Partial Dates

Element	Reporting Detail
General	
 • Partial dates will be displayed as captured in subject listing displays.
Adverse	
 • The eCRF allows for the possibility of partial dates (i.e., only month and year) to be

Events	
recorded for AE start and end dates; that is, the day of the month may be missing. In such a case, the following conventions will be applied for calculating the time to onset and the duration of the event:
 
 ○ Missing Start Day: First of the month will be used unless this is before the start date of study treatment; in this case the study treatment start date will be used and hence the event is considered On-treatment as per Appendix 4: Study Phases and Treatment Emergent Adverse Events. ○ Missing Stop Day: Last day of the month will be used, unless this is after the stop date of study treatment; in this case the study treatment stop date will be used. ● Completely missing start or end dates will remain missing, with no imputation applied. Consequently, time to onset and duration of such events will be missing.
Concomitant Medications/ Medical History	
 ● Partial dates for any concomitant medications recorded in the CRF will be imputed using the following convention: 
 ○ If the partial date is a start date, a '01' will be used for the day and 'Jan' will be used for the month ○ If the partial date is a stop date, a '28/29/30/31' will be used for the day (dependent on the month and year) and 'Dec' will be used for the month. ● The recorded partial date will be displayed in listings.

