12.10.6. Safety Tables

Safety: Tables					
No.	Population	IDSL / Example Shell	Title	Programming Notes	Deliverable [Priority]
Adverse Events (AEs)					
3.01.	SAFF	SAFE_T01	Overview of On-treatment Adverse Events During the Study		SAC
3.02.	SAFF	AE1	Summary of All On-treatment Adverse Events by System Organ Class and Preferred Term	ICH E3	SAC
3.03.	SAFF	AE1	Summary of All On-treatment Serious Adverse Events by System Organ Class and Preferred Term	ICH E3	SAC
3.04.	SAFF	AE3	Summary of All On-treatment Adverse Events by Overall Frequency	ICH E3, summarise by PT	SAC
Laboratory: Chemistry					
3.05.	SAFF	LB1	Summary of Worst Case Chemistry Results Relative to Normal Range Post-Baseline Relative to Baseline	ICH E3	SAC
Laboratory: Hematology and Cardiac Markers					
3.06.	SAFF	LB1	Summary of Worst Case Hematology and Cardiac Markers Results Relative to Normal Range Post-Baseline Relative to Baseline	ICH E3	SAC

Safety: Tables					
No.	Population	IDSL / Example Shell	Title	Programming Notes	Deliverable [Priority]
ECG and Holter					
3.07.	SAFF	EG1	Summary of ECG Findings	IDSL	SAC
3.08.	SAFF	EG11	Summary of Maximum Increase in QTcF Values Post-Baseline Relative to Baseline by Category	IDSL	SAC
3.09.	SAFF	HM1	Summary of Holter Interpretations	IDSL	SAC
Vital Signs					
3.10.	SAFF	VS1	Summary of Vital Signs	ICH E3	SAC
3.11.	SAFF	VS1	Summary of Change from Baseline in Vital Signs	ICH E3	SAC
3.12.	SAFF	VS1	Summary of Change from Pre-dose to Post-dose in Vital Signs	ICH E3	SAC

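### SAP Section 12.4.1 puts the first-infusion day in Pre-Treatment, against the AE rules in 12.4.3 and 12.7.2.1, and the On-treatment tables are not tied to either rule

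*SAP*

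**What the plan says.** Section 12.4.1 opens with a rule that covers more than AEs: "Assessments and events will be classified according to the time of occurrence relative to study treatment start date". Its table then works on dates alone. Pre-Treatment is "Date ≤ Study Treatment Start Date" and On-Treatment is "Study Treatment Start Date < Date ≤ Study Treatment Stop Date + 28 days".

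Section 12.4.3 defines the treatment-emergent flag as "Study Treatment Start Date ≤ AE Start Date ≤ Study Treatment Stop Date + 28 days". Its note then uses the phase label for AEs: "If the study treatment stop date is missing then the AE will be considered to be On-Treatment".

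Section 12.7.2.1 deals with AE start dates whose day is missing. If the first of the month falls before treatment began, "in this case the study treatment start date will be used and hence the event is considered On-treatment as per" Appendix 4, the appendix that holds both 12.4.1 and 12.4.3.

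On outputs, the safety endpoint in Section 2.2 is treatment-emergent AEs. Tables 3.01–3.04 in Section 12.10.6 use the other label, for example "Summary of All On-treatment Adverse Events by System Organ Class and Preferred Term". Section 8.1 refers only to the sponsor's core data standards. Tables 6.01 and 6.02 (free and total sST2) have On-treatment in brackets in their titles, while Section 10.1 sets no phase limit.

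**The concern.** Two sections of one appendix give opposite answers for an AE that starts on the day of the first infusion, and a third section cites that appendix for an answer its phase table does not give. The endpoint is worded in the terms of 12.4.3, and the tables are labelled in the terms of 12.4.1. A programmer who takes the defined On-Treatment phase at face value would leave first-infusion-day AEs out of every AE summary table. The plan's AEs of special interest include hypersensitivity and anaphylactic reaction, so the infusion day is a poor day to lose.

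For assessments, no other phase rule competes with 12.4.1. A post-dose sample or reading taken on Day 1 is Pre-Treatment by its wording.

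**Working it through.** The plan gives no figure to reproduce here. The check applies each rule literally to the days around its boundaries.

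**Inputs.** First dose is on Day 1 and last dose on Day 57 (Weeks 0 and 8 in the Section 12.2.1 schedule). The stop date is taken as the last dose date, so stop date + 28 = Day 85. The choice of stop date does not affect the comparison, because 12.4.1 and 12.4.3 share the same upper limit.

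| Day | 12.4.1 phase | 12.4.3 flag | 12.4.2 phase (medication starting that day) |
|---|---|---|---|
| −1 | Pre | not emergent | Pre |
| **1** | **Pre** | **emergent** | **On** |
| 2 | On | emergent | On |
| 57 | On | emergent | On |
| 85 | On | emergent | On |
| 86 | Post | not emergent | Post |

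The 12.4.1 On-Treatment window is (start, stop + 28] and the 12.4.3 window is [start, stop + 28]. They differ by one date, the start date. A partial AE date moved to the start date under 12.7.2.1 is Pre-Treatment under 12.4.1 and emergent under 12.4.3. Section 12.4.2 governs concomitant medication only. It is shown because it draws the line where 12.4.3 does.

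**Size for AEs.**
- Study treatment is given at V3, V5 and V6, so the disputed date is 1 of 3 infusion days.
- Section 2.1 says the study ended before 20 subjects were randomised, so at most 19 were randomised and no arm can exceed 19.
- One subject whose only AE began on that date changes the arm's any-AE percentage by at least 1/19 = 0.0526, or 5.3 percentage points.
- The document does not say how many such subjects there are. The only bound is 0 to 19.

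**Size for sST2.**
- The schedule calls for pre- and post-dose samples at Week 0 and Week 8 and a pre-dose sample only at Week 4. Post-dose samples must be taken within 4 hours of the end of infusion, so the Week 0 one almost certainly carries the first-dose date.
- Under 12.4.1 it is Pre-Treatment. That is 1 of the 2 samples labelled post-dose.
- Counting every sample after the first dose through Week 12 (Week 0 post, Week 2, Week 4 pre, Week 8 pre, Week 8 post, Week 12), it is 1 of 6.

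**Other Day 1 data.** Vital signs are also taken before and after the dose at V3, and Section 12.6.3 plans on-treatment maximum and minimum values. The Day 1 post-dose readings meet the same problem.

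**The case against.** For AEs, the document goes a long way towards settling its own intent. Section 12.4.3 is the only AE-specific rule, and it includes the start date both in words and as a formula. Its note and Section 12.7.2.1 both use On-treatment in that sense, and a specific rule normally prevails over a general one. This stands as evidence of intent. It does not remove the defect: 12.4.1 names events without exception, no text ranks one rule above the other, and the note in 12.4.3 covers only a missing stop date.

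For sST2 the objection is stronger. Section 12.5.2 bases summaries on planned time relative to dosing, and Section 12.3.1 uses nominal visits. The bracketed On-treatment in Tables 6.01–6.02 may be there only to exclude the Week 24 follow-up sample. A strict 12.4.1 filter would also strip out the Day 1 pre-dose raw values, which suggests that no such filter was meant. The less-than-or-equal sign also fits Section 5.2, which treats untimed Day 1 values as pre-dose baseline. So the misclassification of the sample is literal, but its loss from the tables happens only if the titles are programmed through 12.4.1.

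The lead-in to 12.4.1 does speak of time of occurrence, but the definitions beneath it compare dates and use no clock time or dose label.

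Finally, the effect is small. Every summary is descriptive, and Listing 13 shows all AEs whatever their phase. This limits the harm, and it stands.

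**Conclusion.** The contradiction is real and confined to one date, the day of the first infusion. On that date 12.4.1 is the outlier against 12.4.3 and 12.7.2.1, and nothing in the SAP expressly says which rule the On-treatment AE tables follow. If 12.4.1 is followed, AEs starting that day leave the only AE summary tables, at a weight of at least 5.3 percentage points per subject affected. The first post-infusion sST2 sample could also leave its tables.

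This rests on three assumptions: that nobody was randomised after the termination described in Section 2.1, that the Week 0 post-dose sample was taken on the dosing date, and, for any effect on tables, that the label is programmed through 12.4.1. No inference is affected, because none is planned. The point should still be fixed: descriptive safety tables are a main output of a trial stopped this early, and two programmers could now produce different ones from the same text.

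**What to change.** Make three changes to the SAP:

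1. In 12.4.1, for events, define Pre-Treatment as date < start date and On-Treatment as start date ≤ date ≤ stop date + 28 days, as in 12.4.3.
2. For assessments on Day 1, classify by the nominal pre- or post-dose label or by time. Pre-dose and untimed values stay Pre-Treatment and remain eligible as baseline under Section 5.2. Values labelled post-dose become On-Treatment.
3. State in Section 8.1 or in the programming notes that Tables 3.01–3.04 use the 12.4.3 treatment-emergent flag.

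With these changes the AE rules agree on every boundary day in the table above, and the Week 0 post-dose sST2 sample falls in the On-treatment tables while the pre-dose sample stays as baseline. The cost is one inequality, one Day 1 split, one pointer and one phase derivation in the analysis datasets. No new data are needed.
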